9.4 Ancillary Treatments

Participants who experience withdrawal symptoms or nausea associated with detoxification and induction may be treated with ancillary medications (see guidelines in study SOPs). Depression is also common in opioid-dependent participants and, though not causally related to XR-NTX use, may adversely affect prognosis of naltrexone treatment (Sullivan, Rothenberg et al. 2006). Participants who show depressive symptoms may be treated by their HIV clinic providers with antidepressants and/or referred for mental health evaluation and treatment.

9.5 Provisions for Access to Investigational Treatment after Study

Prior to the conclusion of the 16 week active treatment phase, the research team will make an effort to arrange for continued treatment with XR-NTX as locally appropriate. In most cases, the study physician will continue to prescribe this FDA-approved study medication as the participant's HIV primary care provider. Where this is not possible (due to insurance or availability of treatment resources, etc.), alternative treatment referrals (e.g., methadone maintenance, intensive outpatient psychosocial aftercare), special access programs, and manufacturer medication assistance plans will be made as appropriate.

9.6 Drug Packaging/ XR-NTX

Drug Packaging/ XR-NTX will be supplied in single use kits. Each kit will contain one 380 mg vial of Vivitrol® microspheres, one vial containing 4 mL (to deliver 3.4 mL) diluent for the suspension of Vivitrol®, one 5-mL prepackaged syringe, one 1-inch 20-gauge needle, two 1.5-inch 20-gauge needles and two 2-inch 20-gauge needles with needle protection devices. Lot number and medication expiration date will be included on the kit labels as supplied by the manufacturer.

9.7 Participant Discontinuation

All participants will be followed for the duration of the study (17-24 weeks, depending on length of time required for completion of screening, detoxification, and induction procedures) unless they withdraw consent, or the investigator or sponsor decides to discontinue their enrollment for any reason. Reasons for the investigator or sponsor terminating a participant from the study may include, but are not limited to, the participant becoming a threat to self or others, lack of funding, or DSMB early termination of the study for safety or effectiveness reasons.

9.8 Blinding

CTN-0055 is an unblinded study.

9.9 Participant Compensation

Participants will be compensated for their time and effort for baseline and follow-up visits. Participants may receive a maximum amount of up to approximately \$410.00 US Dollars for completing the following activities: screening interview, baseline assessment, and visits at 1, 4, 8, 12, and 16 weeks.. The specific amounts and format (e.g., cash, debit card, voucher, etc.), and distribution schedule will be determined by the participating site with the approval of the lead investigator or co-lead investigators and the corresponding IRB(s) of record.

10.0 STUDY ASSESSMENTS AND INSTRUMENTS

The selected assessments attempt to balance the value of comprehensive data against the costs of data collection in terms of staff time, feasibility of completing assessments in an outpatient HIV clinic setting, financial cost, and response burden. Therefore, assessments have been limited to those that contribute directly to the study objectives or that are necessary for reasons of safety or regulatory compliance. When choosing between comparable instruments, we have chosen instruments for which CRFs have already been built for other recent CTN trials to minimize the cost of new CRF construction.

10.1 List of all CRF's and Table of Assessments

Assessment/Activity	Associated CRF	Pre-Screening	Screening	Baseline	Randomization	Week 0 (induction)	Week 1	Week 4	Week 8	Week 12	Week 16	End of Treatment (≠Week 16)	As Needed Only
Inclusion/Exclusion checklist	ENR-B				X								
Informed Consent/HIPAA	ENR-A		X										
Inventory Form	INV												X
Locator Form			X	X	X	X	X	X	X	X	X	X	
Master Enrollment Log			X	X									
Medical Release			X										X
Missed Visit Form	MFV												X
Pre-Screening Interview	PSI	X											
Progress Note Checklist			X	X	X	X	X	X	X	X	X	X	
Protocol Deviation	PDV												X
Screening Log		X											
Study Termination	STT										X	X	
Visit Compensation Log			X	X	X	X	X	X	X	X	X	X	
General Measures													
Demographics	DEM		X										
Quality of Life, from PhenX	QLP			X							X	X	
Tobacco Use History, from PhenX	TUH			X							X	X	
Safety & Medical Measures													
Adverse Events	AD1-3												X
ARV Medication Log	ARV			X							X	X	
CBC	LAB		X										
CD4 Count	LAB				X			X		X	X	X	
Confirmed Pregnancy and Outcome	PRG,PO1- 4												X
Detoxification	DTX					X							

Assessment/Activity	Associated CRF	Pre-Screening	Screening	Baseline	Randomization	Week 0 (induction)	Week 1	Week 4	Week 8	Week 12	Week 16	End of Treatment (≠Week 16)	As Needed Only
ECG Results	ECG		X										
Ethyl Glucuronide	UDS		X				X	X	X	X	X	X	
Fatal Overdose	FOD										X	X	
Vital Signs (blood pressure, pulse, temperature, height, and weight)	VIS		X								X	X	
Hepatitis B surface antigen (HBs AG)	LAB				X								
Hepatitis C virus antibody (HCV ab)	LAB				X								
Hepatitis C pcr confirmation, when HCV ab +	LAB												X
HIV-1 RNA PCR	LAB				X			X	X	X	X	X	
Injection Site Abnormality	INA												X
Injection Site Examination	INX						X	X	X	X	X	X	
LFT (AST, ALT) and INR	LAB		X				X	X	X	X	X	X	
Medical and Psychiatric History	MHX		X										
Medication Adherence	MAD			X				X	X	X	X	X	
Pain Assessment	PEG			X				X	X	X	X	X	
Naloxone Challenge	NXC					X*							
Non-Fatal Overdose	NFO			X							X	X	
PBMC	LAB				X			X					
Physical Examination	PEX		X										
Pregnancy and Birth Control Assessment	PBC		X			X	X	X	X	X	X	X	
UDS	UDS		X			X	X	X	X	X	X	X	
XR-NTX administration log	INJ					X		X	X	X			
XR-NTX Injection						X		X	X	X			
Drug Use, HIV & Psychological Measures													
ASI Lite Drug/Alcohol Use	ASD			X							X	X	
Concise Health Risk Tracking	CHRT			X		X	X	X	X	X	X	X	

Assessment/Activity	Associated CRF	Pre-Screening	Screening	Baseline	Randomization	Week 0 (induction)	Week 1	Week 4	Week 8	Week 12	Week 16	End of Treatment (#Week 16)	As Needed Only
DSM-5 Substance Use Disorders	DSM		X										
HIV Care Utilization	HCU			X							X	X	
Medication Assisted Treatment	MAT			X				X	X	X	X	X	
Readiness for Substance Drug Treatment	RST			X							X	X	
Risk Assessment Battery	RAB			X				X	X	X	X	X	
Timeline Follow Back	T55			X		X	X	X	X	X	X	X	
Treatment Plan	TXP				X	X		X	X	X	X	X	
Treatment Satisfaction	TTS										X	X	
Treatment Services Review	TSR			X		X		X	X	X	X	X	
Visual Analog Scale	VAS			X				X	X	X	X	X	

* Only for participants randomized to the XR-NTX arm

11.0 GENERAL MEASURES

11.1 Implementation Assessment

The Western States Node has led the analysis of Site Influences on Treatment Effects (SITE) for prior CTN trials. To assess provider and site characteristics, the SITE instruments and procedures will be modified to fit the CTN-0055 design. During pre-implementation visits to potential study sites, the SITE survey will be completed with study interventionists (physicians, nurses and counselors) and site variables will be assessed through an interview with the clinical director. The Interventionist Survey assesses training, demographics, and attitudes toward the use of buprenorphine, extended-release naltrexone, and methadone for treatment of opioid use disorders among HIV infected individuals who use opioids.

11.2 Inclusion/Exclusion

This form will include each inclusion and exclusion criterion to document eligibility. Eligibility will be assessed continually as appropriate. Only participants who continue to meet study eligibility criteria will be allowed to continue with the screening process and randomization.

11.3 Locator Form

A locator form will be used to obtain information to assist in finding participants during treatment and at follow-up. This form will collect participants' current address, email address, and phone numbers. In order to facilitate locating participants if direct contact efforts are unsuccessful, we will collect addresses and phone numbers of 2-3 family/friends, who may know how to reach the participant, as well as information such as Social Security number, driver's license number, social media, and other information to aid in searches of public records. This information will be collected at screening, and will be updated at each visit. No information from this form will be used in data analyses.

11.4 PhenX Core Tier 1 Form

The Substance Abuse and Addiction Collection of the PhenX Toolkit (www.phenxtoolkit.org) includes highly recommended measures that are being adopted across NIDA-funded research (National Institute on Drug Abuse 2012). The Core Tier 1 collection includes measures for demographics (age, ethnicity, gender, race, educational attainment, employment status and marital status), BMI, quality of life, and HIV Risk & Status; substance use measures include age of onset, past 30-day quantity and frequency, lifetime use for alcohol, tobacco and other substances. We will delete Core Tier 1 Items regarding HIV testing, since only HIV-infected participants are eligible for the current study. Where possible, answers to Core Tier 1 questions will be populated from the answers to questions from other assessments. Core Tier 1 assessments will be completed at Baseline only, with selected items repeated at week 16 (or the end-of-medication/end-of-treatment visit if medication or TAU intervention is stopped early).

11.5 Demographics Form

The demographics form will collect information about demographic characteristics of the participant, including gender, date of birth, ethnicity, race, education, employment pattern, and marital status. The PhenX Core Tier 1 form will be completed during the screening process to collect demographic data.

11.6 Treatment Satisfaction Survey

Satisfaction with treatment will be recorded on the Treatment Satisfaction Survey completed at the end-of-medication visit (if medication is stopped early), the end-of-treatment visit (if TAU intervention stopped early), or the week 16 visit (for participants who complete study participation).

11.7 End of Medication/End of Treatment Form

This form tracks the participant's status with regard to the study intervention/medication. It will be completed at the end-of-medication visit (if XR-NTX is stopped early), the end-of-treatment visit (if TAU intervention is stopped early), or at the week 16 visit (for participants who complete study participation).

11.8 Study Termination Form

This form tracks the participant's status in the study. It will be completed at the week 16 visit or once the week 16 visit window elapses for participants who do not complete this final visit. This form will be used in data analyses to address variables such as treatment retention and completion.

12.0 SAFETY AND MEDICAL MEASURES

The study clinician must review and approve all safety and eligibility assessments in order to confirm participant eligibility prior to randomization.

12.1 Medical and Psychiatric History

The study clinician will obtain a medical and psychiatric history from the participant covering past and present health conditions to help determine eligibility and to provide baseline information. This form will be collected during screening. Information from this form may be used in data analyses.

12.2 Physical Exam

The study clinician will complete a physical examination at screening, to ensure that there are no medical concerns regarding participation and to gather baseline information regarding the participant's physical health. During the screening physical exam, a description of the participant's body habitus will be documented and the study medical clinician will examine the planned injection sites to ensure adequacy for XR-NTX gluteal intramuscular injection of naltrexone with the supplied needle.

12.3 Vital Signs

Study personnel will complete vital signs (blood pressure, pulse, temperature, height, and weight) to inform overall medical fitness for participation, along with the physical exam.

12.4 Electrocardiogram (ECG)

A 12-lead ECG will be administered by appropriately qualified and trained medical personnel at screening, and assessed by a study clinician. The results of ECG tests conducted within 30 days prior to randomization will be acceptable. The screening ECG will assist in determining participant eligibility.

12.5 DSM-5 Checklist

The DSM-5 Checklist is a semi-structured, interviewer administered instrument that provides current diagnoses for substance use disorders based on DSM-5 diagnostic criteria. The DSM-5 Checklist will be completed at screening to determine eligibility. Participants will also indicate their preference substance if they use both opioids and alcohol.

12.6 Clinical Laboratory Tests

Trained staff will be responsible for collecting and processing biologic specimens. Local laboratories at participating pilot sites will be used to conduct laboratory tests. Laboratories must be accredited by the College of American Pathologists (CAP) or equivalent, and participate in the Clinical Laboratory Improvement Act of 1998 (CLIA) or equivalent evidence of laboratory certification. Laboratories will provide reference ranges and proof of laboratory certification.

HIV-1 RNA PCR: will be drawn following randomization, and at 4, 8, 12, and 16 week follow-up visits (or end-of-medication/end-of-treatment if medication or TAU intervention stopped early) for outcomes assessment.

CD4 Count (T-helper cells): will be drawn following randomization and at 4, 8, 12, and 16 week visits (or end-of-medication/end-of-treatment if medication or TAU intervention stopped early) for secondary outcomes assessment.

Peripheral Blood Mononuclear Cells (PBMCs): For all participants, we will collect 4 CPT tubes for PBMC analysis following randomization and at the Week 4 visit or the first blood draw following study drug initiation. PBMC analysis will be conducted in a related NIH application to assess the effects of opioid blockade on TLR mediated immune responses. Samples must be drawn during CTN-0055 study implementation, but may be analyzed at a later time.

Safety labs: AST, ALT, CBC, INR, and urine pregnancy test (for females) will be performed to help determine eligibility at screening. Receipt and review of laboratory test results is necessary before confirming eligibility, conducting randomization and starting study medication. Results of laboratory tests conducted within 30 days prior to randomization (e.g., collected as part of routine detoxification admission) will be acceptable.

Liver profile: (AST, ALT, INR) will be repeated 1 week after study treatment initiation and at 4, 8, 12, and 16 week visits (or end-of-medication/end-of-treatment if medication or TAU intervention stopped early).

Hepatitis: Following randomization, blood will be collected for hepatitis B surface antigen (HBsAG) and Hepatitis C virus antibody (HCVab). These tests do not determine eligibility and will only be conducted on samples from subjects who are randomized. Results of laboratory tests conducted within 90 days prior to randomization (e.g., collected as part of routine detoxification admission) will be acceptable. If needed Hepatitis C pcr confirmation will be performed, when HCVab is positive.

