13.3 Addiction Severity Index-lite (ASI-Lite)

The ASI-Lite is derived from the Fifth Edition of the ASI (McLellan, Kushner et al. 1992), a structured clinical interview that yields scores for seven areas of functioning typically impacted by addiction, including medical status, employment status, drug use, alcohol use, family status, legal status, and psychiatric status. Only the drug use and alcohol use sections of the ASI-Lite will be used. Opioid and alcohol use questions, including the main type of opioid used by the participant, whether a prescription opioid or heroin, the onset of the use, the participant's perception of the substance that is most problematic, and their present treatment goal will also be assessed at baseline as part of the ASI-Lite assessment. The ASI-Lite drug and alcohol sections will be completed at baseline and 16 weeks (or end of medication/end-of-treatment visit if medication or TAU intervention is stopped early) for assessment of secondary outcomes.

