15.2 Non-Fatal Overdose

Non-fatal overdoses in the past 4 weeks will be assessed using a self-reported instrument used in previous studies at baseline and 16 weeks or the end-of-medication visit (if medication is stopped early) (Coffin, Tracy et al. 2007). Overdose events are sentinel events that are less likely to be prone to recall bias than other events. If non-fatal overdose resulted in adverse event, it should also be captured on the AE/SAE CRF.

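### The protocol lets an early end-of-treatment visit stand in for the week 16 assessment of secondary outcomes, against its own rule that all participants are followed for the full study

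*Protocol*

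**What the plan says.** Two sets of instructions stand in the protocol.

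**Week 16 or the early visit.** Section 12.6 places the HIV-1 RNA draws at weeks 4, 8, 12 and "16 week follow-up visits (or end-of-medication/end-of-treatment if medication or TAU intervention stopped early) for outcomes assessment". CD4 and the liver profile follow the same pattern there. So do the urine drug screen (13.1), ethyl glucuronide (13.2), timeline follow-back (13.4), craving (13.5), treatment services and medication use (13.6, 13.7), CHRT-SR (13.8) and readiness (13.10). For ASI-Lite, 13.3 says "16 weeks (or end of medication/end-of-treatment visit if medication or TAU intervention is stopped early) for assessment of secondary outcomes". ART adherence (14.1), risk behaviour (14.3) and non-fatal overdose (15.2) name only the end-of-medication visit; 15.2 reads "at baseline and 16 weeks or the end-of-medication visit (if medication is stopped early". Sections 11.6 and 11.7 list three alternative occasions, the last being, in 11.7, "or at the week 16 visit (for participants who complete study participation". Table 10.1 has a separate column headed "End of Treatment (≠Week 16" and ticks the Study Termination form under that column as well as under Week 16.

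**Full follow-up.** Section 9.7 states: "All participants will be followed for the duration of the study", unless consent is withdrawn or the investigator or sponsor ends the participant's enrollment. Section 11.8 says of the Study Termination form: "It will be completed at the week 16 visit or once the week 16 visit window elapses". Section 23.1.5.4, on pregnancy, expects participants who come off medication to keep attending visits. Section 7.4 keeps following incarcerated participants whose study treatment is stopped.

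The secondary outcomes (5.2, 8.2, 17.2) are set at week 16 or, for opioid abstinence, over the last 30 days of the 16 weeks. Section 17.6 analyses participants in the arm assigned and plans no special handling of missing data.

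**The concern.** A site that follows the either/or wording takes the final outcome measurements when treatment stops and may then close the participant's record. Whether a secondary outcome is measured at week 16 would then depend on staying on treatment. That is a post-randomization event, and retention on treatment is itself one of the outcomes the arms are compared on. An analysis by assigned arm needs the week 16 value whether or not treatment continued, and no analysis plan can recover measurements that were never taken.

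The effect need not be equal across arms. After XR-NTX the drug blocks opioid effects for weeks, so an early visit can record a state that no longer holds at week 16. In 14.1, 14.3 and 15.2 the substitution names only the end-of-medication visit, which 11.7 links to stopping XR-NTX and distinguishes from the end-of-treatment visit for TAU. Read literally, the two arms would be assessed at different times for those measures.

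The secondary objectives exist to supply point estimates (5.2) for a multisite trial, and 6.3 discusses such a trial with viral suppression as its primary outcome. Estimates taken at mixed times, or only in those still on treatment, would serve that purpose poorly.

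**Working it through.** The protocol states no figure on this point, so there is none to reproduce. The check compares passages and counts days.

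**1. Do the passages agree?** They do not. Under 11.7, 12.6, 13.3 and 15.2 the early visit is an alternative to week 16. Under 9.7, 11.8 and 23.1.5.4 the participant stays in the study to week 16. In Table 10.1 the separate column is compatible with two visits, and no note says that one replaces the other. The Study Termination tick in that column, however, contradicts 11.8. No section fixes the day of the end-of-treatment visit. Only for liver enzymes does 17.5 say that a last available measurement may serve instead of week 16.

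**2. Where could an early visit fall relative to blockade?** Inputs: injections at weeks 0, 4, 8 and 12 (9.3.3.3); essentially complete blockade for 30 days (4.2), or full blockade to 5 weeks = 35 days (9.3.3.4); restart allowed up to 3 weeks after a missed dose (9.3.3.4).

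- On the date of a missed dose: day 28 after the last injection, inside both durations.
- At the restart limit: 28 + 21 = day 49, past both.
- At true week 16, (16 − week of last injection) × 7 gives day 112, 84 or 56 for a last injection at week 0, 4 or 8, all past both.
- For a completer injected at week 12: (16 − 12) × 7 = day 28 at week 16.

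An early visit may thus fall inside or outside full blockade. A stopper's true week 16 falls outside it whenever the last injection was at week 8 or before.

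**3. Example for overdose.** Section 15.2 asks about the past 4 weeks; the outcome runs from screening to week 16. Take a last injection at week 4 and an end-of-medication visit at week 8. The recall covers weeks 4 to 8, days 0 to 28 after injection, all under blockade. This instrument would not ask about weeks 8 to 16. A week 16 visit would cover weeks 12 to 16, days 56 to 84.

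**4. How many?** The protocol gives no 16-week stopping rate. As an assumption, take 20% to 47%. The upper end is 1 − 0.53, from the 6-month XR-NTX retention in the cited Russian trial (4.2), which had a different population and a longer period. With 50 participants: 0.20 × 50 = 10 and 0.47 × 50 = 23.5, about 24. Those counts include people lost to follow-up, who would lack week 16 data under any wording. The participants the wording actually affects, stoppers who can still be reached, are fewer by an unknown number.

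**The case against.** The strongest reply is that the protocol already answers the question. Sections 9.7, 11.8, 23.1.5.4 and 7.4 all point to continued follow-up. Sections 22.9 and 23.1.5.3 describe the end-of-medication visit as serving safety and end-of-medication outcomes, not week 16 outcomes. The schedule keeps the two visits in separate columns. Which value is analysed as week 16 is also commonly left to a statistical analysis plan, which is not shown. The secondary analyses are declared hypothesis-generating (17.5).

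Much of this stands. A reader might infer that stoppers simply have no week 16 outcome; no section says so, and several say the opposite. A reader might also infer that XR-NTX stoppers are measured under blockade. The documents do not support that as a fact: the visit day is open, a visit held once restart is ruled out would fall past full blockade, and completers are themselves at day 28 at week 16. For completers, though, that is their real week 16 state, whereas for an early stopper it is not. The point also has no bearing on drinking outcomes in alcohol-only participants.

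Partial cover exists. Record abstraction up to 24 weeks after randomization includes viral load, CD4, liver enzymes and overdose events (9.2.5). ART prescription and HIV visits come from records (14.1, 14.2), and fatal overdose is sought by chart review in those lost (15.3). Records do not replace study urine tests, daily self-reported use, or overdoses that never reached care.

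The reply does not remove the conflict. The either/or wording recurs across most outcome instruments, the termination tick supports early close-out, and 23.1.5.4 sits under pregnancy only. What is collected is a matter for the protocol, not the analysis plan.

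**Conclusion.** The point holds as a contradiction that must be reconciled. Participants who stop treatment but remain reachable may have an early value or none for HIV RNA, CD4, opioid and alcohol use, and self-reported non-fatal overdose. For XR-NTX stoppers the early visit may lie within the stated 30-day or 5-week blockade and so miss later opioid use or overdose.

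Treatment initiation and retention are not affected. The size cannot be fixed from the protocol: the 10 to about 24 of 50 rests wholly on an assumed stopping rate and is a ceiling under that assumption. It should not be read as the number of week 16 values lost through this wording. The conclusion itself needs no rate; it rests on the texts and on the fact that some participants will stop early, for which the protocol itself provides.

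**What to change.** - In 11.6–11.7, 12.6, 13.1–13.8, 13.10, 14.1, 14.3 and 15.2, replace *or* with *and, in addition, at end of medication/treatment*.
- State that the scheduled assessments continue through week 16 for participants who stop treatment, in both arms.
- In Table 10.1, limit the Study Termination tick in the End of Treatment column to withdrawal of consent or termination by the investigator or sponsor, so that it agrees with 9.7 and 11.8.
- State that an end-of-treatment value is not used as the week 16 value for week 16 secondary outcomes, except where the protocol says otherwise, as 17.5 does for liver enzymes.

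These changes concern data collection only and leave treatment decisions untouched. They cost an edit to the protocol and schedule, plus some extra tracing, visits and compensation for early stoppers, which the follow-up rule in 9.7 already implies. They will not recover participants who are lost to follow-up.
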